4.0 Test Schedule

Cycle length = 28 days.

Tests and procedures	Active Monitoring Cycle length = 28 days +/- 7 day window for study visits and tests. ⁵				
	≤21 days prior to randomization	Prior to each new cycle (≤7 days)	Prior to 3 rd and subsequent odd cycles (5, 7, 9, etc.)	At PD, withdrawal, removal, or end of protocol treatment	Observation (Clinical follow-up)
Informed Consent	X				
History and exam, wt., ECOG PS	X	X		X	X
Height	X				
Adverse event assessment	X	X ⁶		X	X
Echocardiogram (2D M-Mode)	X ⁸				
Hematology: CBC/ differential	X	X ⁵		X	X
Chemistry: SGOT (AST), alk phos, T. bili, creatinine, calcium, phos, glucose, Na, K, ALT, GFR, LDH ¹¹	X	X ^{4,5}		X	X
G6PD test	X ^{R, 9}				
Urinalysis	X			X	
Thyroid function test (TSH)	X		X		
Coagulation test: INR, APTT	X				
Tumor measurement	X ¹		X ¹		X ^{1, 10}
CT/MRI brain, if needed (See Section 3.29a)	X		X		
Bone scan ¹²	X		X		
ECG	X		X		
Pregnancy test (serum)	X ²				
Mandatory archival tissue collection (see Section 17.2)	X ^{R, 7}				
Patient Medication Diary (Appendix II)		X ³		X ³	

¹ CT chest, abdomen, and pelvis with IV contrast. If unable to receive IV contrast, MRI abdomen/pelvis with contrast and CT chest without contrast are acceptable. Use same imaging method throughout the study.

- ² For individuals of childbearing potential only. Must be done ≤ 7 days prior to randomization.
- ³ The diary must begin the day the patient starts taking the medication and must be completed per protocol and returned to the treating institution every 4 weeks.
- ⁴ For ARM- A (ascorbic acid group) only: Draw at baseline then weekly for Cycle 1, then for subsequent cycles on Day 14 and Day 28. For ARM B only: draw at baseline then once every cycle.
- ⁵ Labs do not have to be repeated prior to Cycle 1 if they were done ≤ 5 days prior to cycle.
- ⁶ Starting with Cycle 2, AE's for Cycle 1 are assessed prior to the beginning of Cycle 2 and are recorded under Cycle 1 AE, following this format for all subsequent cycles.
- ⁷ Receipt of archival tumor tissue (if available) is not required for study randomization and initiation of therapy. . However, it is mandatory to receive the required tissue ≤ 30 days from registration.
- ⁸ Echocardiogram done ≤ 6 months prior to randomization is acceptable.

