8.12 Dose Modifications for Pazopanib at Time of Treatment

→ → Use the NCI Common Terminology Criteria for Adverse Events (CTCAE) version 4.0* unless otherwise specified ← ←			
CTCAE System/Organ/Class (SOC)	ADVERSE EVENT	AGENT	ACTION**
BASED ON INTERVAL ADVERSE EVENT			
Investigations	Platelet count decreased Grade 3 or 4	Pazopanib	Omit until \leq Grade 2 then restart at next lower dose level. If no recovery to grade 2, discontinue
Investigations	
Prolongation of QTc Interval (If the QTc is prolonged, the ECG should be manually read to ensure accuracy of the reading. The values below refer to manually read ECGs.)
 
QTc \geq 480 < 500 msec
 
QTc \geq 500 msec
	Pazopanib	
Continue pazopanib; monitor as clinically indicated. Consider reducing Pazopanib dose to dose level 1 and gradually increase as tolerated. Recommend discontinuing any other QT prolonging agent in the patient's medication list.
 
Interrupt Pazopanib and discontinue any other QT prolonging agent in the patient's medication list. Recheck EKG in 1 week, If < 500msec, restart Pazopanib at dose level 2 with close monitoring. If recurrent/ refractory QTc > 500msec, discontinue pazopanib and continue follow-up per protocol.

Renal and urinary disorders	Creatinine \geq Grade 3	Pazopanib	Omit until < Grade 3 then restart at next lower dose level. If \geq Grade 3 recurs, reduce one dose level again until no dose can be given (see Section 8.2 regarding ascorbic acid dose reduction)

→ → Use the NCI Common Terminology Criteria for Adverse Events (CTCAE) version 4.0* unless otherwise specified ← ←			
CTCAE System/Organ/ Class (SOC)	ADVERSE EVENT	AGENT	ACTION**
	Proteinuria UPC <3 UPC ≥3 or 24-h urine protein ≥3g	Pazopanib	Continue pazopanib at the current dose; monitor as clinically indicated 1. Interrupt pazopanib. 2. Weekly UPC or 24-hr urine protein monitoring until UPC is <3 or 24-hr urine protein is <3 grams. Then restart pazopanib dose-reduced by 200 mg. 3. If UPC ≥3 or 24-h urine protein ≥3g recurs, repeat steps 1 and 2. 4. If UPC ≥3 or 24-hr urine protein ≥3 recurs and the pazopanib dose can no longer be reduced, discontinue pazopanib and continue follow-up per protocol.

→ → Use the NCI Common Terminology Criteria for Adverse Events (CTCAE) version 4.0* unless otherwise specified ← ←				
CTCAE System/Organ/Class (SOC)	ADVERSE EVENT	AGENT	ACTION**	

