8.13 Dose Modifications for Pazopanib at Time of Retreatment

→ → Use the NCI Common Terminology Criteria for Adverse Events (CTCAE) version 4.0* unless otherwise specified ← ←			
CTCAE System/Organ/Class (SOC)	ADVERSE EVENT	AGENT	ACTION**
AT TIME OF RETREATMENT			
Investigations	Platelet count decreased Grade 3 or 4	Pazopanib	Hold until ≤ Grade 2 then restart at next lower dose level. If no recovery to grade 2, discontinue
Investigations	Electrocardiogram QT corrected interval prolonged ≥ 500msec Grade 3	Pazopanib	Discontinue pazopanib
Renal and urinary disorders	Creatinine > Grade 3	Pazopanib	Hold until < Grade 3 then restart at next lower dose level. If ≥ Grade 3 recurs, dose reduce again until no dose can be given

→ → Use the NCI Common Terminology Criteria for Adverse Events (CTCAE) version 4.0* unless otherwise specified ← ←			
CTCAE System/Organ/Class (SOC)	ADVERSE EVENT	AGENT	ACTION**
Vascular disorders	Thromboembolic event DVT/PE Grade 3 Grade 4 Arterial Thrombosis/Ischemia Any Grade	Pazopanib	Hold and initiate anticoagulant. Decrease 1 dose level if 
 • Subject must have been treated at desired level of anticoagulation for at least 1 week • No Grade 3 or 4 or clinically significant Grade 2, hemorrhagic events have occurred while on anticoagulation treatment. Note: When treating with warfarin, INR S/B monitored within 3 to 5 days after any change in pazopanib dosing and then at least weekly until INR is stable. The dose of warfarin may need to be adjusted to maintain the desired level of anticoagulation. Discontinue pazopanib Discontinue pazopanib
Vascular disorders	Hypertension	Pazopanib	See table 8.3
Gastrointestinal disorders	GI bleed Grade 2 Grade 3 or 4	Pazopanib	Interrupt pazopanib, restart at dose level 2 when bleeding has resolved and gradually titrate up as tolerated. Discontinue Pazopanib
Respiratory, thoracic and mediastinal disorders	Pulmonary bleed Grade 2 Grade 3 or 4	Pazopanib	Interrupt pazopanib, restart at dose level 2 when bleeding has resolved and gradually titrate up as tolerated. Discontinue Pazopanib

→ → Use the NCI Common Terminology Criteria for Adverse Events (CTCAE) version 4.0* unless otherwise specified ← ←			
CTCAE System/Organ/Class (SOC)	ADVERSE EVENT	AGENT	ACTION**

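### For a first QTc of 500 msec or more, section 8.12 restarts pazopanib at 400 mg after recovery and section 8.13 stops it for good; a scheduled ECG can meet both rows and nothing says which governs

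*Combined protocol and SAP*

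**What the plan says.** Section 8.12 covers adverse events in the interval since the last treatment. At QTc 500 msec or more the site interrupts pazopanib, stops other QT-prolonging agents and repeats the ECG in one week. If the value is below 500 msec, the site is to "restart Pazopanib at dose level 2 with close monitoring". Pazopanib is discontinued only if the prolongation is recurrent or refractory. The row adds a condition on the reading: "The values below refer to manually read ECGs".

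Section 8.13 covers the time of retreatment. Its row is "Electrocardiogram QT corrected interval prolonged ≥ 500msec Grade 3" and its action is to discontinue pazopanib, which the table footnote defines as stopping treatment completely. It mentions no manual reading, no repeat ECG and no distinction between a first and a later event.

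Section 8.1.1 lists levels -1 (600 mg) and -2 (400 mg), so dose level 2 in the QTc row can only mean 400 mg. Section 7.1 gives the retreatment interval as 28 days. Section 4.0 marks the on-treatment ECG in the column for the third cycle "and subsequent odd cycles (5, 7, 9, etc", under a general heading of "28 days +/- 7 day window for study visits and tests".

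**The concern.** The two rows share a threshold and give opposite instructions on whether the patient may receive the drug again. Two sites reading the same tracing could act differently, each following a written rule: one ends pazopanib permanently, the other resumes it at half dose after recovery.

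The choice also touches the primary endpoint. Under section 16.11, going off protocol treatment for an adverse event is a treatment failure, whereas an interruption followed by a restart is not. In Arm B pazopanib is the only agent, so permanent discontinuation for QTc is a TFF40 failure. The documents do not say whether an Arm A patient could continue ascorbic acid alone.

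**Working it through.** **1. Can one ECG meet both rows?** Treatment lasts 10 cycles, so the scheduled on-treatment ECGs come before cycles 3, 5, 7 and 9, four in all. Each falls at a retreatment point. The 7-day window lets the tracing fall inside the preceding interval, and footnote 6 of section 4.0 records adverse events assessed before a cycle under the cycle just ended. That footnote governs recording rather than dosing, so it supports the overlap without settling it. Neither section 7 nor section 8 says which table takes precedence.

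**2. Is 8.13 limited to rechallenge?** Its other rows say not. Grade 3 DVT/PE reads "Hold and initiate anticoagulant. Decrease 1 dose level if", which manages a new clot. The grade 2 GI and pulmonary bleed rows read "Interrupt pazopanib, restart at dose level 2 when bleeding has resolved and gradually titrate up as tolerated", the same action as in 8.12. The creatinine row treats recurrence as a separate step: "If ≥ Grade 3 recurs, dose reduce again until no dose can be given".

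**3. Rows present in both tables.**

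| Row | First event, 8.12 vs 8.13 | Recurrence, 8.12 vs 8.13 |
|---|---|---|
| QTc 500 msec or more | restart at 400 mg vs stop | stop vs stop |
| Platelets, grade 3-4 | restart vs restart | stop (thrombocytopenia row) vs no such stop |
| Pulmonary bleed, grade 2 | restart vs restart | stop vs no such stop |
| GI bleed, grade 2 | restart vs restart | no separate rule in either |
| Creatinine; dermatitis, grade 2 | restart vs restart | no conflict on restart or stop |
| DVT/PE, grade 3 | restart vs restart | no separate rule in either |
| DVT/PE, grade 4; arterial thrombosis; GI or pulmonary bleed, grade 3-4; dermatitis, grade 3 | stop vs stop | not applicable |
| All other, grade 2-3 | restart 200 mg lower vs hold, restart dose not given | no separate rule in either |
| All other, grade 4 | stop vs stop | not applicable |

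QTc is the only first-event conflict. In the two recurrence mismatches, 8.13 is the more permissive table. The thrombocytopenia stop sits in a second entry of 8.12; the platelet-count entry in 8.12 has no recurrence stop either.

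**4. Size for TFF40.** The documents give no rate for QTc of 500 msec or more; section 15.17 lists QT prolongation of any degree at 1% to 10%. I assume r = 0.5%, 1% and 2%.

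- Expected cases: 82 × r = 0.41, 0.82, 1.64.
- Chance of at least one case: 1 − (1 − r)^82 = 33.7%, 56.1%, 80.9%.
- Expected loss in Arm B TFF40 if every case is stopped: 45% × r = 0.23, 0.45, 0.90 points. One patient is 1/41 = 2.4 points.

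Power in section 16.21 reproduces: SE = √[(0.45×0.55 + 0.64×0.36)/41] = 0.108; 0.19/0.108 − 0.878 = 0.88; power 81%. Exact enumeration of the section 16.3 rule (un-pooled z, one-sided 0.19, 41 per arm) gives 83.4% because the data are discrete. I use 83.4% only as the baseline below. Each would-be success becomes a failure with probability r, independently of outcome, in both arms:

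| r | Decision changes (Arm A 45 / 55 / 64%) | Declared promising at 64% |
|---|---|---|
| 0.5% | 1.1 / 1.6 / 1.2% | 83.2% |
| 1% | 2.0 / 3.0 / 2.1% | 82.9% |
| 2% | 3.6 / 5.2 / 3.6% | 82.5% |

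If half the cases are stopped, the decision changes in 0.6% to 3.0%. If only Arm B stops count as failures, it changes in 0.3% to 3.2%, the lower end with half the cases stopped.

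**The case against.** The best defence is that the tables work in sequence. An interval event leads to interruption and a one-week recheck; if QTc is still or again at 500 msec when the drug is due to resume, 8.13 stops it, much as the recurrent-or-refractory clause in 8.12 does. The headings allow this, but step 2 shows that 8.13 also manages first events, and its QTc row does not limit itself to recurrences.

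A second defence is that the headings divide the tables by timing, so 8.13 alone governs a pre-cycle ECG. Then a first event found on a scheduled ECG ends pazopanib for good, while the same event on an unscheduled mid-cycle ECG allows a restart. The protocol gives no reason for that difference.

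A third is that 8.13 adds a Grade 3 label, so the triggers may not be identical. Whether the grade adds a condition depends on the CTCAE text, which is not in the documents. The row itself states 500 msec. Nor does its silence on manual reading show that an unchecked automated value would be enough.

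Two parts of the opposing case stand. The tables also differ on recurrent pulmonary bleed and recurrent thrombocytopenia, so correcting QTc alone would leave them unreconciled. The TFF40 figures rest on an assumed rate and are upper bounds: they treat every case as stopped under 8.13, although 8.12 would itself stop the recurrent and refractory ones.

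**Conclusion.** The contradiction is real and should be corrected: opposite instructions for a first QTc of 500 msec or more, an overlap at the scheduled ECGs, and no precedence rule. The finding rests on the text and needs no event rate.

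Three stronger readings are tempting, and the documents do not support them. A reader might infer that patients are dosed unsafely; both rules stop dosing at once, and 8.12 restarts only after a recheck below 500 msec. A reader might infer bias between arms; the pazopanib rules and ECG schedule are the same in both. A reader might infer that the trial's conclusion is at risk. At assumed rates of 0.5% to 2% the decision changes in at most 5.2% of trials, that figure arising with Arm A at 55%; at the 64% design alternative the maximum is 3.6%. The probability of declaring Arm A promising moves by at most 0.9 points. The reason to act is the contradictory cardiac-safety instruction.

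**What to change.** Make the 8.13 QTc row refer to the 8.12 rule: manual reading, interrupt, stop other QT-prolonging agents, recheck in one week, restart at Dose Level -2 if below 500 msec, discontinue if recurrent or refractory. The study chair should confirm that this was intended. If discontinuation at the first event was intended, change 8.12 to match instead. Also add the 8.12 recurrence stops to the 8.13 pulmonary-bleed and platelet rows. As an optional clarification, give the restart dose (200 mg lower) in the 8.13 row for all other grade 2-3 events.

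This edits a few table cells and changes no visit, sample size or analysis. Each choice has a clinical cost. The 8.12 rule re-exposes some patients at 400 mg after QTc has recovered to below 500 msec. The 8.13 rule permanently takes pazopanib from some patients whose QTc recovers.

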Vascular disorders	Thromboembolic event	Pazopanib	
Continue pazopanib at the current dose; monitor as clinically indicated
	
	DVT/PE			
	Grade 2			
	Grade 3			
Omit and initiate anticoagulant. Restart at reduced dose if
 
 • Subject must have been treated at desired level of anticoagulation for at least 1 week • No Grade 3 or 4 or clinically significant Grade 2, hemorrhagic events have occurred while on anticoagulation treatment. 
Note: When treating with warfarin, INR S/B monitored within 3 to 5 days after any change in pazopanib dosing and then at least weekly until INR is stable. The dose of warfarin may need to be adjusted to maintain the desired level of anticoagulation.

	Grade 4			Discontinue pazopanib
Arterial Thrombosis/Ischemia Any Grade	Discontinue pazopanib			
	Thrombocytopenia: Investigate and document underlying cause		
Continue pazopanib with current dose; monitor as clinically indicated.
 
Step 1. Interrupt pazopanib until toxicity resolves to ≤ Grade 2. Step 2. Restart pazopanib dose-reduced by 200 mg and monitor as clinically indicated.
 
If no recovery to ≤ Grade 2 or recurrent Grade 3 or 4 thrombocytopenia, discontinue Pazopanib and follow-up per protocol.
	
	Grade 1 or 2			
	Grade 3 or 4			

→ → Use the NCI Common Terminology Criteria for Adverse Events (CTCAE) version 4.0* unless otherwise specified ← ←			
CTCAE System/Organ/Class (SOC)	ADVERSE EVENT	AGENT	ACTION**
Vascular disorders	
Hypertension (Scenario A)
 
Asymptomatic and persistent^d SBP of ≥ 140 and < 160 mmHg, or DBP ≥ 90 and < 100 mmHg,
 
Or
 
Clinically significant increase in DBP of 20 mmHg (but still below 110 mmHg).
	Pazopanib	
 • Continue pazopanib treatment at the current dose • Adjust current or initiate new antihypertensive medication • Titrate antihypertensive medication(s) during the next 2 weeks as indicated to achieve well-controlled BP • If BP is not well controlled within 2 weeks, consider referral to a specialist and go to scenario (B).

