	
(Scenario B)
 
Asymptomatic SBP ≥ 160 mmHg, or DBP ≥ 100 mmHg,
 
Or
 
Failure to achieve well-controlled BP within 2 weeks in Scenario A
	Pazopanib	
 • Interrupt pazopanib treatment if clinically indicated • Adjust current or initiate new antihypertensive medication(s) • Titrate antihypertensive medication(s) during the next 2 weeks as indicated to achieve well-controlled BP • Once BP is well controlled^e, restart pazopanib treatment reduced by one dose level

→ → Use the NCI Common Terminology Criteria for Adverse Events (CTCAE) version 4.0* unless otherwise specified ← ←			
CTCAE System/Organ/Class (SOC)	ADVERSE EVENT	AGENT	ACTION**
	Symptomatic ^f hypertension or Persistent ^g SBP ≥160 mmHg, or DBP ≥100 mmHg, despite antihypertensive medication and dose reduction of study treatment	Pazopanib	
 • Interrupt pazopanib treatment • Adjust current or initiate new antihypertensive medication(s) • Titrate antihypertensive medication during the next 2 weeks as indicated to achieve well-controlled BP • Referral to a specialist for further evaluation and follow-up is recommended Once BP is well controlled, restart pazopanib treatment reduced by one dose level
	Refractory hypertension unresponsive to above interventions.	Pazopanib	
 • Permanently discontinue pazopanib treatment • Continue follow-up per protocol.

→ → Use the NCI Common Terminology Criteria for Adverse Events (CTCAE) version 4.0* unless otherwise specified ← ←				
CTCAE System/Organ/Class (SOC)	ADVERSE EVENT	AGENT	ACTION**	
Cardiac Disorders	LVEF-drop (%) or CTCAE grade	Pazopanib	
 • Interrupt pazopanib study treatment and repeat ECHO within 2 weeks^b and monitor and control BP. • If the LVEF recovers within 4 weeks (defined as LVEF \geqLLN and absolute decrease \leq10% compared to baseline) 
 -Restart study treatment^f reduced by one dose level (Contact ACCRU if there are any questions prior to restarting) -Repeat ECHO 2 , 4 , 8 and 12 weeks after re-start; monitor BP; continue in intervals of 12 weeks thereafter • If repeat LVEF does not recover within 4 weeks 
 -Consult with cardiologist -Permanently discontinue pazopanib treatment Repeat ECHO after 2, 4, 8, 12, and 16 weeks or until resolution. (Contact ACCRU if there are any questions) 	

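### In 8.12, Scenario A's diastolic-rise criterion runs to 110 mmHg while Scenario B starts at 100 mmHg, so some patients meet both rows and nothing says which governs pazopanib

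*Combined protocol and SAP*

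**What the plan says.** Section 8.12 handles hypertension in four rows of rising severity: Scenario A, Scenario B, symptomatic or persistent hypertension, and refractory hypertension.

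- **Scenario A** has two limbs. The first is asymptomatic, persistent pressure with "SBP of ≥ 140 and < 160 mmHg, or DBP ≥ 90 and < 100 mmHg". The second, an alternative, is "Clinically significant increase in DBP of 20 mmHg (but still below 110 mmHg". The pazopanib action is "Continue pazopanib treatment at the current dose", with antihypertensives adjusted and titrated over two weeks. The last bullet reads "If BP is not well controlled within 2 weeks, consider referral to a specialist and go to scenario (B".
- **Scenario B** covers "Asymptomatic SBP ≥ 160 mmHg, or DBP ≥ 100 mmHg", or failure to reach control in two weeks under A. The pazopanib action is "Interrupt pazopanib treatment if clinically indicated", with the same antihypertensive steps, and then, once pressure is controlled, "restart pazopanib treatment reduced by one dose level".

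Footnote d defines persistent, in A's first limb, as two separate readings over up to three consecutive visits. Scenario B has no such condition. Section 8.1.1 sets the dose levels at 800, 600 and 400 mg daily.

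**The concern.** A dose-modification table should send each patient to one row. Here Scenario A's second limb reaches 10 mmHg into the diastolic range where Scenario B has already begun, and the two rows give different pazopanib instructions. A site that reads A keeps the dose. A site that reads B may interrupt and restart one level lower. Both would be following the protocol.

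Section 15.17 lists hypertension among the common toxicities of pazopanib (above 10%), so these rows are likely to be used. What is at stake is consistent dosing between sites for the same presentation. One written rule also tells the site to carry on unchanged at a pressure that the next row treats as more severe.

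**Working it through.** There is no design figure to reproduce; the check is on the logic of the rules.

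**Inputs, all from 8.12.** The patient is asymptomatic.

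- A, first limb: 140 ≤ SBP < 160 or 90 ≤ DBP < 100, persistent (footnote d).
- A, rise limb: DBP − reference ≥ 20 and DBP < 110.
- B: SBP ≥ 160 or DBP ≥ 100.

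Two assumptions are needed. The text gives no reference point for the rise, so study baseline is used, and a rise of 20 is read as at least 20. The rise is also taken to be clinically significant, as the limb requires.

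**Main overlap: the rise limb.** A's cap and B's floor leave DBP 100 to 109 in both rows whenever the rise is at least 20.

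| Reading | Reference DBP | Rise | Scenario A | Scenario B |
|---|---|---|---|---|
| 130/104 | 82 | 104 − 82 = 22 | met (rise limb) | met (DBP) |
| 170/105 | 85 | 105 − 85 = 20 | met (rise limb) | met (both) |
| 165/88 | 68 | 88 − 68 = 20 | met (rise limb) | met (SBP) |
| 130/102 | 85 | 102 − 85 = 17 | not met | met (DBP) |

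The last line is a control: with a rise under 20 and SBP outside 140 to 159, only B applies. The layout does not show whether footnote d also governs the rise limb. If it does, a single reading of 130/104 meets only B, and the overlap begins when the reading is confirmed.

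**Secondary overlap: the or between SBP and DBP.** Once the elevation is persistent, 150/102 meets A by SBP and B by DBP. Likewise 165/95 meets A by DBP and B by SBP. Before a second reading, A's first limb is not met and B alone applies, unless the rise limb is also met.

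**Search for a ranking rule.** Footnotes d to g define terms only. Section 7.21 gives general rules for reduction and re-escalation. The hypertension row of 8.13 points to a table 8.3 that is not in the text. The nursing guidance in 15.19 does not rank the rows. A's hand-off to B after two weeks is sequential and does not say which row applies on the day. The appendices are redacted, so a rule there cannot be excluded, but the hypertension rows cite none.

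**Test of the fix**, taking persistence as met:

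- Lowering A's cap to below 100 sends 130/104 and 170/105 (with the rises above) to B only. It leaves 150/102, 150/112, 165/95, and 165/88 from 68 in both rows.
- Adding precedence for B at SBP ≥ 160 or DBP ≥ 100 removes every overlap, because every overlapping reading meets B by one of those limits. No reading loses its row, because only readings already in B are moved out of A.

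**Size of the dose difference.** At a first event it is 800 mg under A versus 600 mg under B after interruption, or 800 − 600 = 200 mg daily. Section 7.21 allows re-escalation.

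**The case against.** The strongest reply is that the table is a ladder. A hands up to B, B lists failure under A as one of its triggers, and an experienced investigator would place a patient who meets B's threshold in B. As a guess about practice that is fair, and it largely settles 150/102 and 165/95: a new reading is in B before A's first limb can be met, and a patient already in A who reaches 150/102 has escalated. A reader might infer that such readings are in conflict as soon as they are taken. The persistence condition in footnote d does not support that, unless the rise limb is also met.

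The ladder does not rescue the rise limb. If B always governed from DBP 100 upward, a cap of 110 in A would have no effect between 100 and 109, since all those readings are already in B. Either the cap is wrong, or A is meant to govern some of those patients, and a site cannot tell which.

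The second reply is that the actions are nearly compatible: B's interruption is discretionary, and its lower dose is worded as a restart. This stands, and it limits the consequence. A reader might infer that the same patient automatically receives 800 mg at one site and 600 mg at another; the text makes that depend on the investigator choosing to interrupt.

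**Conclusion.** The point holds for the rise limb: as written, 8.12 gives two pazopanib instructions for DBP 100 to 109 with a qualifying rise, and no text ranks them. The overlap from the or is real but secondary, and needs persistence. The rule is wrong as written, and minor.

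This rests on the two assumptions stated for the rise. If footnote d governs the rise limb, the conflict at DBP 100 to 109 starts at confirmation instead of at the first reading. The documents give no blood pressure distribution, so the number of patients affected is unknown.

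A reader might go on to infer a bias in the primary endpoint. The documents do not support it: neither row discontinues pazopanib, and 16.11 does not count dose reduction or interruption as treatment failure. No effect on TFF40, power or error rates is claimed.

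**What to change.** In 8.12, make two changes together:

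1. In Scenario A, change the cap on the rise limb from below 110 mmHg to below 100 mmHg.
2. Add one line to the hypertension rows: *Scenario B takes precedence over Scenario A whenever SBP is ≥ 160 or DBP is ≥ 100 mmHg.*

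The line should rank A against B only. The symptomatic or persistent row, which applies at these same pressures "despite antihypertensive medication and dose reduction of study treatment", and the refractory row stay as they are.

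The same amendment could state the reference point for the 20 mmHg rise and whether footnote d applies to it. It could also say whether B's one-level reduction applies when pazopanib was not interrupted, and redirect the hypertension cross-reference in 8.13 to the rows of 8.12.

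The cost is one line and a few words in the next amendment, with no new visits, tests or patients.
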